The low tear interchange rate reported by Polse suggests that if corneal edema is to be prevented with contact lens wear, the material must have high enough oxygen transmissibility to meet the oxygen needs of the cornea. This observation is consistent with the predictions by Fatt and Lin (Fatt I L. D., 1976) and Fatt and Hill (Fatt I H. R., 1970), who have shown that the contribution of tear flow to the oxygen tension at the anterior cornea for most low Dk/t hydrogel lenses would be as low as 4 mmHg. Many currently used hydrogel contact lenses can only supply adequate oxygen to the cornea directly by diffusion if the lens thickness is less than 0.10 mm (Decker M, 1978).

Study Objective

- I. Evaluate corneal oxygen uptake of a new translating contact lens design with comparison to published data and commercially available designs.
- II. Evaluate subjectively reported comfort of a new translating contact lens design with comparison to commercially available designs.

[figure not shown]
Hypothesis

We hypothesize that the Apioc lens design will provide greater tear exchange behind this novel soft contact lens than a standard soft contact lens. Its patented design suspends the lens from the upper eyelid thus allowing a looser fit and greater movement of the contact lens over the ocular surface than standard thickness soft contact lenses. These design aspects should lead to an increase in tear exchange behind the contact lens. Because tear exchange behind a soft contact lens is very difficult to measure on the human eye, and there is no tear exchange rate benchmark that is correlated with direct clinical benefits, the impact of the Apioc contact lens design will be assessed indirectly by measuring corneal oxygen uptake, as the cornea receives its oxygenation through the tears. Thus, our experimental hypothesis is that the cornea wearing the Apioc contact lens will have an oxygen uptake rate of ≥ 10 mm Hg.

Apioc is manufactured in Definitive 74 contact lens material (Dk/t = 44) (Benjamin, 2018). If the Apioc contact lens and standard contact lens have center thickness of 0.20 mm, then the Dk/t of the lenses is 22 which correlates with 9 percent EOP. If the Apioc lens movement with blinking at a normal blink rate allows greater oxygen delivery by 30 percent to 12 percent EOP, (See illustration by Benjamin below) it will allow normal corneal thickness, (prohibit corneal swelling) in daily wear. This provides a clinical benchmark demonstrating

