that the Apioc contact lens design will provide an improvement in corneal physiology over the standard soft contact lens design.

Note, lenses having an Equivalent Oxygen Percentage (EOP) of 9.9%, do not induce corneal edema. Holden and Mertz (Holden BA, 1984) state an oxygen transmissibility of at least $24.1 \pm 2.7 \times 10^9$ (cm X ml C>2)/(sec X ml X mmHg) which correlates closely with Benjamin, above.

Study Lenses

The Apioc contact lens is a daily wear soft contact lens, which is classified under 21 CFR 886.5925 (product code: LPL). The FDA has previously made risk determinations (class II, non-significant risk) for devices classified under 21 CFR 886.5925. The Apioc-A contact lens has the same actions and indications for use as other contact lenses classified under 21 CFR 886.5925. As a non-significant risk device, the Apioc contact lens is exempt from the IDE regulation (21 CFR 812).

Subject Qualification

Number of Subjects

The total number of enrolled subjects will be 10. This is a common sample size for corneal oxygen uptake studies.

Inclusion Criteria

Prior to enrollment in the study, the following criteria must be met by each prospective subject:

1. Provide informed consent.
2. Appear willing and able to adhere to instructions set forth in the protocol.
3. Be between the ages of 18 and 45.
4. Be an experienced contact lens wearer.
5. Be an eyecare clinician or clinician-in-training.
6. Flat and steep keratometry readings within 40 to 50D.
7. Clear, healthy corneas with no irregular astigmatism.
8. Normal, healthy conjunctiva in both eyes.
9. Be able to provide corneal topography measurements.
10. Be able to provide manifest refraction measurements.

Exclusion Criteria

1. Irregular corneal astigmatism.
2. Use of topical or systemic antihistamines within the previous week.
3. Use of topical ophthalmic drops within the previous two days.
4. History of corneal surgery.
5. Currently pregnant or lactating.
6. Systemic disease that would interfere with contact lens wear.
7. Previous diagnosis of dry eye syndrome.

Study Design and Procedures

Study Design

Structure: Single center, serially recruited

Duration: approximately one month from consent to study completion

Visit Schedule: up to three study visits separated by a minimum of 48 hours

Clinical Study Methods

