In this study, an experienced clinician will apply the oxygen electrode as described above to one eye of up to 10 subjects who are experienced contact lens wearers, eyecare clinicians or clinicians-in-training, and have no active ocular conditions that would preclude short term contact lens wear.

There will be up to five scenarios that will be examined at each visit: cornea with no stimulus to represents the high oxygen condition; immediately after gently closing their eyes for 5 minutes to represent the low oxygen condition; and after contact lens wear. Lens options include Apioc lens design with lenticular, Apioc lens design without lenticular, and commercially available contact lenses. The contact lens conditions will be worn with normal blinking – every four seconds for five minutes prior to oxygen uptake measures. The scenarios will be randomized to minimize bias.

Each of these measurements lasts less than one minute and are repeated at two additional visits.

A rest period of at least ten minutes of normal open eye blinking should be allowed between measurements of the same eye.

The conjunctiva of the subject will be examined prior to probe applications and between probe applications to assess ocular irritation induced by the probe. An increase in two grades on to the Brien Holden Vision Institute Grading Scales (see appendix) will indicate a need to discontinue measurements for the day.

Screening

- I. Statement of Informed Consent
 - A. Prior to enrollment, each subject must read, understand, and sign the informed consent document. It must also be signed by a study team member who is authorized to consent subjects.
 - B. Each subject must be given a signed version of this document.
- II. Eligibility
 - A. All criteria must be met.
 - B. All responses to Inclusion Criteria must be “yes.”
 - C. All responses to Exclusion Criteria must be “no.”

III. Demographics – Age (in years and months)

Baseline Visual and Ocular Assessment

- I. Measure presenting visual acuities: OD, OS
- II. Anterior segment slit lamp examination
 - A. Ocular abnormalities noted
 - B. Eligibility – examiner will determine if subject continues to meet inclusion/exclusion criteria

Oxygen Consumption of the Cornea Measurement

- I. Setup equipment in accordance with the procedure manual.
- II. Instill 1 drop of artificial tears into the eye that will not be measured.
- III. Experimental Conditions
 - A. High oxygen conditions: normal open eye conditions with normal blinking

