 - B. Low oxygen conditions: close both eyes for 5 minutes prior to testing
 - C. Soft contact lens conditions: apply contact lens to test eye and wait at least 5 minutes. Blink to a metronome set at 15 blinks per minute. Remove the contact lens immediately before the probe is applied in step IV below. In one visit, measure up to three different contact lens designs in a randomized order:
 - i. Apioc lens design with lenticular
 - ii. Apioc lens design without lenticular
 - iii. Standard lens design with a thickness equivalent to the mean thickness of the Apioc design with lenticular
 - iv. Commercially available contact lenses
- IV. Collect measurements in accordance with the procedure manual.
 - A. Measurements will be randomized to minimize bias.
 - B. Measurements will be repeated if initial review of data indicates poor quality.
- V. Determine whether the study visit is complete.
 - A. Visually assess conjunctival redness. An increase of two grades in bulbar or limbal redness on the reference grading scales indicates the current study visit is complete.
 - B. Ask the subject to complete the comfort assessment (see Appendix). An answer of “no” to question 2 indicates the current study visit is complete.
 - C. A completion of all measurements listed in the conditions above (A, B, and up to three contact lenses for condition C) indicates the current study visit is complete.
- VI. If another measurement will be collected in the current study visit, a rest period of at least ten minutes of normal open eye blinking will be allowed between measurements of the same eye.

Concluding Visual and Ocular Assessment

- I. Measure visual acuities with presenting correction in place: OD, OS
- II. Anterior segment slit lamp examination
 - A. Ocular abnormalities noted

Corneal Oxygen Uptake Calculation

Calculate the slope over a 100 torr drop in oxygen uptake – from 140 torr to 40 torr.

Data Analysis

The study objective is to compare the corneal oxygen uptake rates of the standard conditions (normal open and closed eyes) and test conditions. Paired t-tests will be performed to determine if this objective is met.

The individual performing data analysis will be masked to minimize bias.

Safety and Adverse Events

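### Neither lens-versus-lens question (Apioc against a commercial lens, Apioc against a standard soft lens) has a planned test, and no stated rule ensures that the standard lens is measured

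*Combined protocol and SAP*

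**What the plan says.** All references are to the combined protocol and SAP.

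- **Study Objective, I:** "Evaluate corneal oxygen uptake of a new translating contact lens design with comparison to published data and commercially available designs". The thickness-matched standard lens is not named.
- **Hypothesis, rationale:** Apioc "will provide greater tear exchange behind this novel soft contact lens than a standard soft contact lens". The section ends with a benchmark, conditional on a 30 percent gain in oxygen delivery, that is said to demonstrate "that the Apioc contact lens design will provide an improvement in corneal physiology over the standard soft contact lens design".
- **Hypothesis, operational form:** "our experimental hypothesis is that the cornea wearing the Apioc contact lens will have an oxygen uptake rate of ≥ 10 mm Hg". This concerns one lens and has no comparator.
- **Clinical Study Methods:** "Lens options include Apioc lens design with lenticular, Apioc lens design without lenticular, and commercially available contact lenses". The standard lens is absent. The section also says: "Each of these measurements lasts less than one minute and are repeated at two additional visits".
- **Oxygen Consumption of the Cornea Measurement, III.C:** "In one visit, measure up to three different contact lens designs in a randomized order". Four types follow: (i) Apioc with lenticular, (ii) Apioc without lenticular, (iii) a standard design matched in thickness to (i), and (iv) commercial lenses.
- **Same section, V.C:** one route to completing a visit is finishing all listed measurements: "A, B, and up to three contact lenses for condition C) indicates the current study visit is complete". No particular lens is required.
- **Data Analysis:** paired t-tests compare the standard conditions, defined in brackets as normal open and closed eyes, with the test conditions.

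**The concern.** The questions that motivate the study compare one lens with another. The analysis compares lenses with the bare eye, open or closed. A result on the second does not answer the first: Apioc could differ from the closed eye, or meet a fixed threshold, and still be no better than a standard or commercial lens.

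The measurement rules add a second gap. Because no lens is mandatory and the two lens lists differ, a study run exactly as written could finish without the data for the standard-lens comparison. If lenses and contrasts are then chosen after the data are seen, the protections that the plan does include, randomization and a masked analyst, lose much of their value for these questions.

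**Working it through.** **Inputs.** 10 subjects (Number of Subjects); up to three visits (Study Design); up to five scenarios per visit (Clinical Study Methods); four lens types with at most three per visit (III.C). The sample size of 10 is justified only as customary. No effect size, SD, alpha or power is given, so it cannot be reproduced.

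**1. Questions against planned tests.**

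- Apioc versus commercial lens (Study Objective, I): no test named.
- Apioc versus standard soft lens (Hypothesis): no test named.
- Apioc against the fixed threshold (Hypothesis): no test named. A one-lens threshold would not rank two lenses in any case.
- Open or closed eye versus test conditions (Data Analysis): paired t-tests.

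Planned lens-versus-lens tests: 0.

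**2. Is the standard-lens pair assured?** Choosing three of four types gives C(4,3) = 4 sets:

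- {i, ii, iii}: contains (i) and (iii)
- {i, iii, iv}: contains (i) and (iii)
- {i, ii, iv}: no (iii)
- {ii, iii, iv}: no (i)

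The set {i, ii, iv} is exactly the Clinical Study Methods list. With open and closed eye it gives 2 + 3 = 5 scenarios, the stated maximum. Used at every visit, it yields 0 of 10 subjects with an (i)-(iii) pair. Either of the first two sets, used throughout and without early completion, yields 10 of 10. Fewer than three lenses is also allowed. The documents support no narrower figure than 0 to 10.

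**3. What lost pairs cost.** This assumes one paired t-test at two-sided alpha 0.05, since the plan states neither alpha nor sidedness. With n pairs and standardized difference d (mean difference divided by the SD of within-subject differences), the statistic is noncentral t with n − 1 degrees of freedom and noncentrality d√n. Solving for 80% power:

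- n = 10: d = 1.00
- n = 5: d = 1.68
- n = 3: d = 3.26
- n = 0: no test

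No SD is given, so these cannot be turned into mmHg/sec.

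**4. Direction.** Background and Introduction says that lowering the oxygen available to the cornea raises the uptake rate above the resting value, which it puts at 3.5 to 4.5 mmHg/sec. More oxygen delivery should therefore mean a lower rate, and improvement means (i) − (iii) < 0. The hypothesis instead sets a lower bound of 10, above the resting range and without the per-second unit. As written, the two statements point in opposite directions.

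**The case against.** The strongest reply is that the standard-lens comparison is rationale rather than objective. The text is conditional, the operational hypothesis is the threshold, and Study Objective I names published data and commercial designs. That is right, and a reader should not infer that a standard-lens comparison is the declared objective. But Study Objective I's own comparison with commercial designs has no named test either, so the gap in the analysis remains.

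Second, a standard soft lens might be taken to include commercial lenses. Then each of the four three-type sets contains an Apioc design and a comparator, and zero pairs no longer follows once three types are measured. This weakens the zero case but does not remove it: three lenses are a ceiling, not a requirement, and there is still no test.

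Third, the general statements that scenarios and measurements will be randomized could be meant to cover the choice of lenses, and the unseen procedure manual could fix it. Both are possible, so the finding is limited to what the supplied text states.

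Two stronger readings are tempting and not supported. One is that the visits clearly have room for all four lens types in every subject. That depends on whether the lens set may change between visits, and Clinical Study Methods can be read as repeating the same set. The other is that matching (iii) on mean thickness, while the hypothesis text assumes equal centre thickness, biases the contrast. No mean thickness is given, so the documents show no such effect.

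**Conclusion.** The point holds as a should-fix matter with medium confidence. The firm part is that no planned test addresses either lens-versus-lens question and that the single-lens threshold cannot stand in for one. This rests on the bracketed definition of the standard conditions in Data Analysis, which excludes reading them as the standard lens.

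The second part is conditional: the number of subjects with an Apioc-versus-standard pair is not assured and could be zero if the Clinical Study Methods list is used at every visit. A reader might infer that the pairs will be missing, but the same text permits all 10, and a selection rule may exist in the procedure manual. The power figures illustrate the cost of lost pairs under an assumed alpha; they do not estimate what this study will achieve.

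**What to change.** 1. Reconcile the lens lists in Clinical Study Methods and in III.C, and say whether the same lens set is repeated at each visit.
2. Require (i), (iii) and one named commercial lens from (iv) in every subject, subject to the existing early-completion rules. As a fixed set this fits the three-lens cap whichever way the repeat-visit sentence is read. If (ii) is also needed, rotate it in at some visits.
3. In Data Analysis, name the paired (i)-versus-(iii) and (i)-versus-(iv) contrasts on subject means over visits, and say which is primary.
4. State which direction of uptake means improvement, and reconcile it with the threshold in the hypothesis.
5. At most, report centre thickness, material and Dk/t of each lens beside the contrasts.

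If the sponsor does not want the standard-lens comparison, withdraw the comparative statement in Hypothesis. Study Objective I would still need its commercial-lens contrast.

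Cost: protocol wording, plus fewer or no measurements of (ii). Measurements are added if fewer than three lenses per visit were intended.

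### Do three visits of at most three lenses leave too few within-subject pairs to compare the four lens categories?

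*Combined protocol and SAP*

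**What the plan says.** Study Design sets the visit schedule at "up to three study visits separated by a minimum of 48 hours", and Number of Subjects says "The total number of enrolled subjects will be 10". Under Oxygen Consumption of the Cornea Measurement, the instruction is "In one visit, measure up to three different contact lens designs in a randomized order". Four categories follow: Apioc with lenticular (i), Apioc without lenticular (ii), "Standard lens design with a thickness equivalent to the mean thickness of the Apioc design with lenticular" (iii), and commercially available lenses (iv).

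Clinical Study Methods is shorter: "Lens options include Apioc lens design with lenticular, Apioc lens design without lenticular, and commercially available contact lenses". It does not mention the thickness-matched standard lens. It then adds: "Each of these measurements lasts less than one minute and are repeated at two additional visits".

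Study Objective I evaluates the new design "with comparison to published data and commercially available designs", and the Hypothesis expects "greater tear exchange behind this novel soft contact lens than a standard soft contact lens". Data Analysis is narrower. It specifies paired t-tests and names only the open-eye and closed-eye reference conditions against the test conditions. It does not list lens-against-lens contrasts, set an alpha, or say how repeat visits become one value per subject.

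**The concern.** Taken literally, the four-lens list, the cap of three lenses per visit, the limit of three visits and the repetition sentence cannot all hold. Something has to give, and the plan does not say what.

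- If each subject keeps the same three lenses at all visits, that subject can inform only three of the six lens contrasts.
- If the lenses change between visits, the repetition sentence is not followed to the letter.
- If only the three categories named in Clinical Study Methods are used, lens iii is never measured.

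Lens iii is arguably the comparator closest to the Hypothesis, and lens iv is the one named in Objective I. Had the schedule really prevented pairing, the number of subjects behind a lens contrast could have been anywhere from 0 to 10, and the planned 10 would have told the reader little about precision.

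**Working it through.** **Inputs.** Lens categories: 4 (procedure list). Lenses per visit: at most 3 (same section). Visits: at most 3 (Study Design). Subjects: 10 (Number of Subjects). Commercially available lenses are counted as one category; this is an assumption.

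**The plan's own figure.** Clinical Study Methods allows up to five scenarios per visit: open eye + closed eye + 3 lenses = 5. This reproduces.

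**Capacity against full repetition.** Slots per subject: 3 visits x 3 lenses = 9. All four categories at every visit: 4 x 3 = 12. The mismatch is real. For the three categories in Clinical Study Methods, 3 x 3 = 9 fits exactly.

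**What one pair per subject needs.** A subject yields a difference for every contrast as soon as each lens has been measured once. That is 4 measurements, which needs two visits at three lenses per visit. The ceiling is 9.

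**Same-visit pairs.** Four lenses give 4 x 3 / 2 = 6 contrasts, and a visit with three lenses supplies 3 of them. Take the visits {i, ii, iii}, {i, ii, iv} and {i, iii, iv}:

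| Contrast | Visits containing both |
|---|---|
| i-ii | 2 |
| i-iii | 2 |
| i-iv | 2 |
| ii-iii | 1 |
| ii-iv | 1 |
| iii-iv | 1 |

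All six are covered. Lens i is measured three times and the others twice (3 + 2 + 2 + 2 = 9). Any schedule that leaves out a different lens at each visit does the same; 4 of the 20 unordered three-visit schedules are of this kind.

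**Fewer visits.** Two full visits with different omissions measure all four lenses and give 5 of 6 same-visit pairs; the sixth can be formed across visits. One visit gives 3 of 6.

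**Tests named in Data Analysis.** Open and closed eye can be measured at every visit. A lens therefore pairs with both at each complete visit where it is worn, and with rotation every lens does so at least twice per subject, in up to 10 subjects.

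**If allocation were left to chance.** Suppose one lens is dropped at random and independently at each of three full visits, giving 4 x 4 x 4 = 64 ordered outcomes. Some lens is never measured only if the same lens is dropped every time: 4/64, so all four are measured in 60/64 = 93.75%. All six same-visit pairs arise when the three dropped lenses differ: 4 x 3 x 2 = 24, and 24/64 = 37.5%.

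**The case for a change.** The best argument for a change is that the allocation is left open, so nothing guarantees the favourable schedule. If the repetition sentence is read strictly, each subject is tied to one trio and supplies 3 of 6 contrasts, so the average contrast has 10 x 3 / 6 = 5 subjects. At an assumed two-sided 5%, the 95% interval half-width would then be 1.24 SD of the difference against 0.72 SD with 10 subjects, and power for a 1 SD difference 40% against 80%. Visits can also end early for redness or at the subject's wish.

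The arithmetic is correct, but it describes only the locked-trio reading. The plan's wording is permissive: visits, scenarios and lenses per visit are all ceilings, and the shorter lens list is introduced as what the options include. Nothing requires every subject to wear all four categories, and nothing ties a subject to a fixed three. The 5 is also a mean over lens-against-lens contrasts, while Data Analysis names tests against the open and closed eye, where the shortfall is smaller.

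A related worry is that visit-level pairs might be analysed as if independent, which would inflate type I error. The plan does not say this will be done, and one averaged difference per subject is the ordinary reading of a paired t-test in 10 subjects.

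What stands is that the two lens lists differ, the repetition sentence cannot hold for four categories, and neither lens-to-visit allocation nor visit averaging is written down.

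**Conclusion.** No change to the plan follows. The count of 12 against 9 is right, but it measures full three-visit repetition of four lenses, not the ability to form pairs. Pairing needs 4 measurements, and the nine slots can give all six lens contrasts a same-visit pair in up to 10 subjects, at the price of unequal repetition (3, 2, 2, 2).

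The remaining points are a clerical mismatch between a summary and a procedural list, and missing detail that a competent analyst supplies without affecting validity: average the within-visit differences to one value per subject, then test. Nor would a stricter rule clearly gain anything. Fixing one trio drops a listed category. Reserving two slots for a favoured contrast and splitting the third between subjects gives 10, 5, 5, 5, 5 and 0 subjects across the six contrasts, which is worse coverage than rotation.

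The conclusion assumes that commercial lenses form one category and that visits are mostly completed. With five or six designs, three visits cover at most 8 of 10 or 9 of 15 same-visit pairs, though every design can still be measured once and paired across visits. A subject with only one visit necessarily misses at least one of the four lenses.

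### Does answering the comfort question after lens removal and probe contact weaken the comfort comparison in Objective II?

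*Combined protocol and SAP*

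**What the plan says.** All steps cited are in the protocol's section Oxygen Consumption of the Cornea Measurement, unless another section is named.

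- **Wear (III.C).** The lens is worn for at least 5 minutes with paced blinking: "Blink to a metronome set at 15 blinks per minute". Clinical Study Methods gives the same pace, "every four seconds for five minutes prior to oxygen uptake measures".
- **Removal (III.C).** "Remove the contact lens immediately before the probe is applied in step IV below".
- **Probe (IV).** The measurement is taken. Under IV.B, "Measurements will be repeated if initial review of data indicates poor quality".
- **Redness, then the form (V.A, V.B).** After redness grading: "Ask the subject to complete the comfort assessment (see Appendix".
- **Rest (VI).** Before any further measurement in the visit, "a rest period of at least ten minutes of normal open eye blinking will be allowed between measurements of the same eye".

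The form in the Appendix has two items. Question 1 is a marked line for the discomfort felt while the lens was on, with an N/A answer. Question 2 asks whether the subject is comfortable having another measurement that day; under V.B a negative answer ends the visit. Question 1 is thus the only described measure for Objective II. Data Analysis names paired t-tests for oxygen uptake and no analysis of comfort.

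**The concern.** The last thing the rated eye feels before question 1 is a sensor on the central cornea, not the lens. The protocol itself treats the probe as a possible irritant: under Clinical Study Methods the conjunctiva is "examined prior to probe applications and between probe applications to assess ocular irritation induced by the probe". A subject asked about discomfort just after that contact might partly rate the probe.

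Probe exposure also need not be identical for every lens. Poor-quality measurements are repeated, and contact ends only once the sensor reading falls below 40 torr, so its length depends on the uptake rate. With at most 10 subjects and one comfort item, extra noise would widen an already imprecise comparison. The apparent remedy is to take question 1 during wear, for example at minute 3 of 5, and to leave question 2 where it is.

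**Working it through.** **1. Order and delay.** The sequence is lens on, lens off, probe, redness grading, form. Question 1 is therefore always answered with the lens off and after at least one contact. Clinical Study Methods puts each measurement at less than one minute, so the recall gap is that plus the redness grading. The past-tense wording fits a rating of the whole wear period given just after it.

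**2. What cancels.** Write a subject's rating of lens A as (subject level) + (effect of lens A) + (probe effect before that rating) + error, and likewise for lens B. The within-subject difference is

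(effect of A − effect of B) + (probe effect before A − probe effect before B) + error.

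The second bracket is zero if the probe adds the same amount each time. Only unequal probing between lenses can shift the comparison. Scenario order is randomised, so probing earlier in the visit does not systematically favour one lens.

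**3. Can the number of contacts just before a rating differ?** Suppose repeats were back-to-back contacts and each measurement needed one repeat with probability p (not in the documents; assume 0.1 to 0.3). Two lenses would then differ with probability 2p(1 − p):

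- p = 0.1: 2 × 0.1 × 0.9 = 18%
- p = 0.3: 2 × 0.3 × 0.7 = 42%

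Step VI does not fit that picture: at least ten minutes of open-eye blinking must separate measurements of the same eye. Step III.C also requires the lens to come off immediately before the probe, so a second contact without new wear would no longer measure the lens condition. A repeat most naturally means rest, new wear and one new contact. Each rating then has exactly one contact directly before it, for every lens, and the 18% to 42% does not arise.

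**4. Can the length of contact differ?** The fall from 140 to 40 mmHg takes 100/rate seconds.

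| Rate (mmHg/sec) | Source | Seconds |
|---|---|---|
| 3.5 | resting, Background | 100/3.5 = 28.6 |
| 4.5 | resting, Background | 100/4.5 = 22.2 |
| 5 | assumed | 100/5 = 20 |
| 8 | assumed | 100/8 = 12.5 |
| 10 | assumed | 100/10 = 10 |

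Lenses at 8 and 10 differ by 2.5 s; lenses at 5 and 10 differ by 10 s. The Background states that uptake after lens wear exceeds the resting rate, so these contacts are shorter than those on the resting eye.

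**5. Precision.** With 10 pairs the 95% half-width is 2.262/√10 = 0.715 SD of the difference. If rating after the probe raised the variance of the difference by 10% or 50%, it would become 0.715 × √1.1 = 0.750 or 0.715 × √1.5 = 0.876, that is 5% or 22% wider. The only document figure here is n = 10. The widening merely restates the assumed variance increase and is no evidence that one exists.

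**6. What a rating during wear would gain and cost.** Clinical Study Methods says "There will be up to five scenarios that will be examined at each visit". With five in random order, a given lens comes first with probability 1/5, so 4/5 of ratings would still follow a probe contact in that visit. At minute 3 of wear that contact would be at least 10 + 3 = 13 minutes old if the rest precedes wear, or 10 − 2 = 8 minutes if wear counts toward the rest.

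The cost falls on the oxygen measurement. Blinking every 4 s is 60/4 = 15 per minute, or 5 × 15 = 75 blinks. A rating of 10 to 20 s (assumed) covers 2.5 to 5 of them, 3.3% to 6.7%. If it starts at minute 3, then 110 to 100 s remain before removal, or 27.5 to 25 blinks. That share is small, but a reading-and-speaking task then sits in the period whose blinking and lens movement are the basis of the Hypothesis section, and any disturbance could differ between lenses.

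**The case for a change.** The strongest case for a change is that it looks nearly free and removes a stimulus the protocol itself watches for irritation from the moments before the only comfort rating. Part of it stands. No rating is taken with the lens on the eye. Step IV.B precedes V and VI in the list, so a reader could take a repeat as immediate reapplication of the probe. Contact length is tied to uptake rate and so could differ systematically by lens. A small residual effect on ratings cannot be excluded. The procedure manual is not among the documents and might add detail on timing.

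This does not add up to a defect. The irritation check concerns the conjunctiva; it is not evidence that subjects attribute probe sensation to the lens. The inclusion criteria require experienced lens wearers who are clinicians or trainees, and the item asks them about the lens. Contact-time differences of seconds do not support a claim about ratings.

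Nor is the alternative plainly better. To keep gaze and blinking steady it would replace a privately marked line with a number spoken to staff; only the data analyst is stated to be masked, so this opens a route for reporting bias. It would also leave the last part of wear unrated. Oxygen uptake is the only outcome with a planned test, and disturbing it to reduce undemonstrated noise in comfort is a poor exchange.

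The absence of any stated analysis for Objective II is a separate matter, and the timing of question 1 does not affect it.

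**Conclusion.** The concern does not hold. Comfort is recorded after lens removal and probe contact, but in the same order for every lens, shortly after wear, and with a question confined to the lens. No directional bias is shown, and the effect on ratings cannot be computed from the documents. The calculable difference in exposure is 2.5 to 10 s of probe contact at the assumed uptake rates. The 5% to 22% wider interval is only an assumed variance increase restated.

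This rests on two readings. A repeat under IV.B is taken to be a further measurement, subject to the ten-minute rest in VI and to new lens wear; and the probe is taken to add roughly the same amount to each rating. If repeats were in fact immediate, the number of contacts could differ between lenses, but any effect on ratings would still be undemonstrated. Timing the question during wear is a possible alternative with its own cost to the oxygen endpoint. The plan needs no change on this point.
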